6.10.3.2.2. Time to Symptom Resolution

Time to symptom resolution is defined (in days) as:

```
(First study day when symptom resolution status is changed to "Yes" – Infusion Date + 1)
```

If a patient has not experienced symptom resolution by completion or early discontinuation of study/study treatment, the patient will be censored at the date of their last visit during the treatment and assessment period. If a patient is hospitalized, the patient will be censored at the date of hospitalization.

Time to symptom resolution will be evaluated during the treatment and assessment period only and will be summarized by treatment and listed. Cox proportional hazard model will be used.

Time to symptom resolution will be presented graphically.

6.10.3.2.3. Time to Sustained Symptom Resolution

For treatment groups 9-14, sustained symptom resolution is defined as 2 consecutive assessments with a score of 0 for shortness of breath, feeling feverish, body aches and pains, sore throat, chills, and headache; and a score of 0 or 1 for cough and fatigue on the symptom questionnaire. Time to sustained symptom resolution is defined (in days) as:

(First study day when sustained symptom resolution status is changed to "Yes" – Infusion Date + 1)

For Treatment Arms 9-11, similar methodology, as described in Section 6.10.3.2.2, will be utilized to perform treatment group comparisons.

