6.3.6. Modified Last Observation Carried Forward

Analyses of symptom data, with the exception of change in symptom score, will utilize a modified last observation analysis (mLOCF). The mLOCF method is performed by carrying forward the last nonmissing postbaseline assessment to the subsequent missing assessments for analysis. For patients who die, all missing collection time points subsequent to the date of death will be imputed to Severe.

After mLOCF imputation, data from participants with nonmissing baseline and at least 1 postbaseline observation will be included in the analyses. The mLOCF imputation helps ensure that the maximum number of randomized participants who were assessed postbaseline will be included in the analyses and unfavorable terminal events are represented.

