6.10.3.2. Symptom Questionnaire

Participants will rate their overall clinical status and severity of symptoms associated with COVID-19 by a daily questionnaire up to Day 11 and on Days 22 and 29. See Appendix 1 for further details regarding the symptoms and overall clinical status participant questionnaire.

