6.10.3.2.4. Symptom Questionnaire AUC

The AUC from Day 1 predose to Day 11 (AUC[0-D11]) will be calculated according to the linear trapezoidal rule using the mean daily Symptom Questionnaire total score. No imputations of

missing data will be conducted. No AUC(0-D11) values will be calculated when Day 1 predose and/or Day 11 values are missing, or if there are more than 1 value missing in the profile.

The Symptom Questionnaire AUC will be summarized and plotted by treatment and listed.

Additionally, Symptom Questionnaire AUC data will be statistically analyzed using a linear model. The model will contain treatment as a fixed effect, baseline symptom total score as a covariate. The LS means and treatment differences (each active treatment group minus placebo) will be calculated and presented with their corresponding 95% CIs. All available data will be used in the analysis.

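### For an outpatient still in the study, mLOCF lets a missed questionnaire supply the confirming assessment for sustained symptom resolution

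*SAP*

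**What the plan says.** SAP Section 6.10.3.2.3 defines the endpoint for Arms 9-14: "sustained symptom resolution is defined as 2 consecutive assessments with a score of 0 for shortness of breath", and likewise for five other symptoms, with cough and fatigue allowed a score of 0 or 1. It does not say that both assessments must be observed. For Arms 9-11 it says that "similar methodology, as described in Section 6.10.3.2.2, will be utilized to perform treatment group comparisons". Section 6.10.3.2.2 sets censoring rules but no imputation rule.

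The missing-data rule comes from Section 6.3.6: "Analyses of symptom data, with the exception of change in symptom score, will utilize a modified last observation analysis (mLOCF"). The method works by "carrying forward the last nonmissing postbaseline assessment to the subsequent missing assessments for analysis". It has one carve-out: "For patients who die, all missing collection time points subsequent to the date of death will be imputed to Severe". Section 6.10.3.2.2 adds a second limit: "If a patient is hospitalized, the patient will be censored at the date of hospitalization". Participants who have not resolved by completion or early discontinuation are censored at their last visit in the treatment and assessment period.

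Symptoms are rated "by a daily questionnaire up to Day 11 and on Days 22 and 29" (Section 6.10.3.2).

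**The concern.** Section 6.10.3.2.1 uses the same symptom scores for simple resolution in Arms 9-14. The second assessment is therefore all that separates sustained from simple resolution. If that assessment can be filled in from the first, the distinction disappears wherever a questionnaire is missing, and missing data can create an event.

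Elsewhere the SAP guards against this. Viral clearance also needs two consecutive results. Under Section 6.3.1 a missing result is imputed as cleared only if two consecutive negatives have already been achieved, and otherwise as not cleared. Section 6.10.3.2.4 turns imputation off for the symptom AUC: "No AUC(0-D11) values will be calculated when Day 1 predose and/or Day 11 values are missing". Sustained resolution has no such safeguard.

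At stake is the meaning of a secondary endpoint that is compared between treatments in Arms 9-11. Arms 12-14 are descriptive only (Section 6.1.4).

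**Working it through.** **Which rule governs.** Section 6.3.6 exempts only change in symptom score. The symptom AUC is exempted in its own section. Sections 6.10.3.2.2 and 6.10.3.2.3 contain no exemption, so mLOCF applies.

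**What the rule does.** Apply mLOCF and then the two-consecutive rule on the schedule of Days 2-11, 22 and 29:

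| Observed pattern | With mLOCF | Next observed assessment must also be resolved |
|---|---|---|
| Resolved Day 5, Day 6 missing, symptoms from Day 7 | Event on Days 5-6 | No event |
| Resolved Day 5, symptoms observed Day 6 | No event | No event |
| Resolved Day 11, Day 22 missing, symptoms Day 29 | Event on Days 11-22 | No event |
| Resolved Day 22, Day 29 missing | Event on Days 22-29 | No event |

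In the first pattern the missed questionnaire alone creates the event; the second row shows that observing the relapse on Day 6 would have prevented it. In the last two patterns one carried value stands in for 22 - 11 = 11 days and 29 - 22 = 7 days. The last pattern assumes that the participant is still in the study. If the Day 29 visit itself was missed, the order of carry-forward and last-visit censoring matters, as it does for dropouts.

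**How often.** The SAP states no missing-questionnaire or relapse rate, so these are assumptions: daily assessments on Days 2-11, probability m that a questionnaire is missing (at random), and probability r that symptoms return the day after a resolved day. After an observed resolved day, mLOCF declares an event with probability D = (1 - m)(1 - r) + m. The share of events with an imputed second assessment is then m/D. The share in which that imputed day hides a relapse is mr/D.

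| m | r | D | m/D | mr/D | False or early, simulated |
|---|---|---|---|---|---|
| 0.05 | 0.10 | 0.905 | 5.5% | 0.6% | 0.5% |
| 0.05 | 0.20 | 0.810 | 6.2% | 1.2% | 1.2% |
| 0.05 | 0.30 | 0.715 | 7.0% | 2.1% | 2.1% |
| 0.10 | 0.10 | 0.910 | 11.0% | 1.1% | 1.0% |
| 0.10 | 0.20 | 0.820 | 12.2% | 2.4% | 2.2% |
| 0.10 | 0.30 | 0.730 | 13.7% | 4.1% | 3.7% |
| 0.20 | 0.10 | 0.920 | 21.7% | 2.2% | 1.8% |
| 0.20 | 0.20 | 0.840 | 23.8% | 4.8% | 4.0% |
| 0.20 | 0.30 | 0.760 | 26.3% | 7.9% | 6.8% |

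The last column comes from a simulation of 200,000 participants with a 10% daily chance of becoming resolved. It counts events declared earlier than the true date or without any true event. It falls slightly below mr/D because some participants had already been truly resolved for two days, with the first of those days unobserved.

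**Effect on the event proportion by Day 11** in the same simulation, at 20% missing:

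| Relapse | True | mLOCF | Both scheduled assessments observed |
|---|---|---|---|
| 20% | 0.521 | about 0.51 | 0.442 |
| 30% | 0.470 | 0.465 | 0.381 |

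**The case against.** The best counter-argument is that, with data missing at random, mLOCF reproduces the overall event proportion well, whereas insisting that both scheduled assessments be observed lowers it by about 8 points (0.521 - 0.442 = 0.079). If people stop reporting because they feel well, an observed-only rule censors them for having recovered. This stands. It shapes the fix, but it does not make a single good day a confirmed recovery.

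Three stronger readings are tempting and are not supported:

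- A reader might infer that mLOCF supplies the second assessment whenever it is missing. It does not: time points after death are set to Severe, hospitalized participants are censored, and only postbaseline values are carried.
- A reader might infer that someone who drops out on the first good day is counted as sustained. Last-visit censoring in Section 6.10.3.2.2 probably prevents this. The SAP does not say which rule takes precedence, nor whether the event is dated at the first or second assessment.
- A reader might take the 6-26% of events with an imputed second assessment as an error rate. Most of those imputed values match the true state; the false or early share is much smaller.

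The endpoint is also one of many secondary endpoints in a study described as nonconfirmatory, without multiplicity control for them (Section 6.5).

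**Conclusion.** The point holds in a limited form. As written, a resolved assessment followed by a missed one meets the definition of sustained resolution for an outpatient still in the study, including when the next observed assessment shows symptoms and across the Day 11-22 and Day 22-29 gaps.

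Under the assumed rates with data missing at random, false or early events are about 0.5-2% at 5% missing, 1-4% at 10% and 2-7% at 20%. These figures cover Days 2-11 only and depend on relapse and missingness rates that the documents do not give. They do not measure bias in the treatment comparison. The Arms 9-11 comparison is biased only if missingness differs by arm or is otherwise informative, and nothing in the SAP shows that it will be. The main harm is that some individual events labelled sustained have not been confirmed.

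**What to change.** State in Sections 6.3.6 and 6.10.3.2.3 that:

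- a carried-forward value cannot serve as the confirming assessment, in line with Section 6.3.1 for viral clearance;
- a resolved assessment followed by a missing one is confirmed only if the next observed assessment is also resolved;
- the event date is a named one of the two assessment dates (Section 6.10 already does this for viral clearance);
- participants without confirmation are censored at the last observed questionnaire, or at hospitalization as Section 6.10.3.2.2 provides.

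Report the mLOCF version as a sensitivity analysis.

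The change is to wording and derivation only; no new data are needed. The cost is fewer and later events where questionnaires are missing, noticeable if missingness reaches about 20%. Every pair confirmed under this rule is also an event under mLOCF, and every pair of adjacent observed resolved assessments still counts. At 20% missing and 20% relapse, the event proportion would therefore lie between 0.442 and about 0.51. Bridging a gap can still hide a brief relapse on the missing day. Informative censoring remains possible if participants stop reporting once well, which is why the mLOCF version should be kept alongside.

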6.10.3.2.4. Symptom Questionnaire AUC

The AUC from Day 1 predose to Day 11 (AUC[0-D11]) will be calculated according to the linear trapezoidal rule using the mean daily Symptom Questionnaire total score. No imputations of

missing data will be conducted. No AUC(0-D11) values will be calculated when Day 1 predose and/or Day 11 values are missing, or if there are more than 1 value missing in the profile.

The Symptom Questionnaire AUC will be summarized and plotted by treatment and listed.

Additionally, Symptom Questionnaire AUC data will be statistically analyzed using a linear model. The model will contain treatment as a fixed effect, baseline symptom total score as a covariate. The LS means and treatment differences (each active treatment group minus placebo) will be calculated and presented with their corresponding 95% CIs. All available data will be used in the analysis.

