Appendix 1. Symptoms and Overall Clinical Status Participant Questionnaire

Participants will rate their overall clinical status and severity of symptoms associated with COVID-19 by a questionnaire. This questionnaire is for outpatient participants only.

Participants will complete 3 questions about their overall clinical status daily, including:

- severity of symptoms
- · general physical health, and
- change in overall health

The questionnaire contains these symptoms

- cough
- shortness of breath
- feeling feverish
- fatigue
- body aches and pain
- sore throat
- chills
- headache
- loss of appetite (yes/no), and
- changes in taste and smell (yes/no)

Each symptom will be scored by the participant as experienced during the past 24 hours.

Symptom and Clinical Status Questionnaire Scores

Rating	Score
None or absent	0
Mild	1
Moderate	2
Severe	3

The Total Symptom Questionnaire score is the sum of the symptoms (excluding the loss of appetite and changes in taste and smell symptoms).

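### The symptom AUC section forbids imputation and requires a Day 11 score, while Section 6.3.6 applies mLOCF to that endpoint; the stricter rule drops participants in hospital on Day 11 or dead by then

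*SAP*

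**What the plan says.** SAP Section 6.3.6 sets the general rule: "Analyses of symptom data, with the exception of change in symptom score, will utilize a modified last observation analysis (mLOCF". Change in symptom score is the only exception named, and the section does not yield to rules stated elsewhere. On death it says: "For patients who die, all missing collection time points subsequent to the date of death will be imputed to Severe". After imputation, "data from participants with nonmissing baseline and at least 1 postbaseline observation will be included in the analyses". Part of the stated aim is that participants assessed after baseline "will be included in the analyses and unfavorable terminal events are represented".

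Section 6.10.3.2.4 computes the symptom AUC from Day 1 predose to Day 11 by the linear trapezoidal rule and rules out imputation: "using the mean daily Symptom Questionnaire total score. No imputations of" (the sentence is cut by a page break; its object is the missing scores). On completeness it states: "No AUC(0-D11) values will be calculated when Day 1 predose and/or Day 11 values are missing". A second condition withholds the AUC "or if there are more than 1 value missing in the profile". The section gives no rule for participants who are in hospital or have died.

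Section 6.10.3.2 makes the questionnaire daily up to Day 11, and Appendix 1 adds: "This questionnaire is for outpatient participants only". Tables PYAH.4.1 and PYAH.4.2 list the symptom AUC as a secondary endpoint for Arms 1-6 and 7-8. Tables PYAH.4.3 and PYAH.4.4 do not list it for the later arms.

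**The concern.** The symptom AUC is an analysis of symptom data and is not the named exception, since change in score has its own section (6.10.3.2.5). Section 6.3.6 therefore tells the programmer to impute and Section 6.10.3.2.4 forbids it. Following one section or the other gives different analysis sets and possibly different estimates.

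The Section 6.10.3.2.4 rule also works against the aim of Section 6.3.6. Hospital days yield no questionnaire score, so a completeness rule on daily scores is partly a rule about staying out of hospital. Admission happens after randomisation, treatment may affect it, and it is itself a secondary endpoint. Dropping participants on that basis compares selected subsets of the randomised groups.

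**Working it through.** The SAP states no figure for this endpoint that could be reproduced. The check sets the rules side by side, works out who is dropped, and then estimates the loss from ordinary missed days.

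**Step 1. The two rules for the same AUC**

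| | Section 6.3.6 | Section 6.10.3.2.4 |
|---|---|---|
| Missing daily score | last post-baseline score carried forward | not imputed |
| After death | Severe | no rule, so missing |
| Needed for an AUC | baseline and at least 1 post-baseline score | Day 1 and Day 11 both present, and at most 1 value missing |

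**Step 2. Who loses the AUC when an absence makes scores missing**

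The profile is Days 1 to 11. Take a run of missed daily scores that starts on any of Days 2 to 11 (10 possible start days) and apply Section 6.10.3.2.4:
- Run of 1 day: the AUC is lost for 1 of 10 start days, namely Day 11 itself.
- Run of 2, 3, 4 or 5 days: the AUC is lost for 10 of 10 start days. Either two or more values are missing, or the run is cut off at Day 11 and so includes Day 11.

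Death by Day 11 that leaves Day 11 unscored also loses the AUC. Participants who are admitted or die after Day 11 keep it, as do those missing a single day before Day 11.

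**Step 3. Ordinary missed days, among participants with a baseline score**

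Assumption, because the SAP gives no missingness rate: each daily score on Days 2 to 11 is missing independently with probability m. An AUC exists if Day 11 is present and at most one of the nine scores on Days 2 to 10 is missing:

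share with AUC = (1 − m) × P(Bin(9, m) ≤ 1), where P(Bin(9, m) ≤ 1) = (1 − m)^9 + 9m(1 − m)^8

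- m = 2%: 0.98 × (0.834 + 0.153) = 0.967, so about 3% lose the AUC.
- m = 5%: 0.95 × (0.630 + 0.299) = 0.882, so about 12% lose it.
- m = 10%: 0.90 × (0.387 + 0.387) = 0.697, so about 30% lose it.

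Under Section 6.3.6 almost all of these participants would keep an AUC, since one post-baseline score is enough. Independence is a simplification. At the same rate, missing days that come in pairs would raise the loss, and missing days concentrated in a few participants would lower it.

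**Step 4. Whether the hospitalisation effect can be sized**

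Let p and q be the placebo and active proportions hospitalised, and let A be the mean AUC if hospitalised against 40 if not. Hospitalised participants then contribute −(p − q)(A − 40) to the active-minus-placebo difference, and excluding them sets that contribution to 0. None of these values is in the SAP. The scale maximum is 8 symptoms × 3 = 24 per day, or 24 × 10 = 240. Taking q = p/3:
- p = 2%, A = 80: −(0.0133)(40) = −0.5
- p = 6%, A = 120: −(0.04)(80) = −3.2
- p = 10%, A = 200: −(0.0667)(160) = −10.7

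The range is about twentyfold and is set entirely by the assumptions. The direction holds if active treatment reduces admissions and hospitalised participants have worse scores.

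**The case against.** The specific section might be read as overriding the general one. That is weak here: Section 6.3.6 lists its own exception and has no clause giving way to other sections. The revision history for Version 4 shows that this rule was revisited and only change in symptom score was exempted.

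It can also be said that the worst outcomes are not lost to the trial. Sections 6.10.3.3.1 and 6.10.3.3.2 analyse hospitalisation and death directly in the safety population, and Section 6.10.3.2.5 analyses daily symptom scores by MMRM on all available data with no Day 11 requirement. This stands, and it limits the consequence for a non-primary endpoint in a Phase 2 study described as nonconfirmatory. It does not settle which rule governs the AUC.

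A reader might infer more than the documents support:
- *That everyone hospitalised, and everyone who dies, is excluded.* The AUC uses Days 1 to 11 only, whereas the clinical-status endpoint runs to Day 29. Step 2 gives the actual extent.
- *That a stated fraction of the treatment effect is lost.* Any such figure needs an AUC for hospitalised participants, and the questionnaire produces no in-hospital scores. Plain mLOCF would carry forward the last pre-admission score, which need not give the high AUCs that such a calculation assumes.
- *That 16% or 37% of participants are lost at 5% or 10% missingness.* Those figures count a missing Day 1 score, but Section 6.3.6 also requires a baseline.
- *That Section 6.3.6 already scores hospital days as Severe.* It does so only after death.

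**Conclusion.** The contradiction is established from the text alone: for the symptom AUC in Arms 1-6 and 7-8, Sections 6.3.6 and 6.10.3.2.4 give incompatible rules. As written, Section 6.10.3.2.4 selects participants partly on a post-randomisation outcome. The resulting bias is probably towards no difference if active treatment reduces admissions, but its size cannot be derived from the SAP. The 12% and 30% losses from ordinary missed days hold under independent missingness at the assumed 5% and 10%. The point deserves correction because one rule undoes the stated purpose of the other. It does not touch the primary endpoint.

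**What to change.** Reconcile the two sections as follows:

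1. In Section 6.10.3.2.4, replace the no-imputation and completeness sentences with a statement that the Section 6.3.6 mLOCF rule, including Severe after death, is applied before the AUC is computed, for everyone with a baseline and at least one post-baseline score.
2. State how in-hospital days are handled. Plain mLOCF carries forward the last pre-admission score and may understate severity. Neither section now covers those days, so any other scoring would be a new rule and should be written as one.
3. Keep the no-imputation, complete-case AUC as a named sensitivity analysis, and report by arm how many participants it excludes and how many of those were in hospital or had died by Day 11.

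If the sponsor prefers to keep Section 6.10.3.2.4, the minimum is to name the AUC as a second exception in Section 6.3.6 and justify the exclusion.

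The cost is SAP wording and programming, with no new data. The downside is reliance on single imputation, as for the other symptom outcomes under Section 6.3.6. The revision history for Version 7 records post hoc analyses on Arms 1-6, so for arms already analysed the change should be labelled as made after data review, with both versions shown.

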6.10.3.2.5. Change in Symptom Questionnaire Score

Change in symptom questionnaire score (total of ratings from those symptoms scored 0-3) from baseline to Days 2, 3, 4, 5, 6, 7, 8, 9, 10, 11, 22, and 29 will be analyzed using an MMRM. The model will contain baseline as a covariate, treatment, day, and treatment-by-day interaction as fixed effects. The LS means and treatment differences (each active treatment group minus placebo) will be calculated and presented with their corresponding 95% CIs. All available data will be used in the analysis.

6.10.3.2.6. Symptom Improvement

Symptom improvement is defined as a patient experiencing both:

- Symptoms on the symptom questionnaire scored as moderate or severe at baseline are subsequently scored as mild or absent, AND
- Symptoms on the symptom questionnaire scored as mild or absent at baseline are subsequently scored as absent.

The proportion of participants that achieve symptom improvement at Days 3, 5, 7, 11, 22, and 29 will be summarized by treatment in frequency tables and listed.

In addition, the number of participants that achieve symptom improvement at days 3, 5, 7, 11, 22, and 29 will be analyzed using logistic regression to compare active treatment versus placebo at each dose level.

Symptom questionnaire data may be collected either through direct data capture (by phone call or in person) or through a paper diary. Symptom improvement may also be analyzed by subgroups for modality.

